We propose a proof of concept study to investigate the acute synergistic effects of active versus sham RIC on motor task training, especially in persons with chronic cSCI. The primary outcome measure will be change in corticospinal excitability after RIC combined with a single bout of isometric hand exercise. The advantage of RIC compared to other current modes of inducing neuroplasticity, such as tDCS and AIH, is that RIC is a more approachable application, because RIC is simple and low-cost. Yet, published studies of RIC regarding neuroplasticity do not exist for populations of individuals with neurologic injury or disease. If synergistic effects of RIC with physical training can be demonstrated in this study, then effects of RIC coupled with various other rehabilitation interventions can be tested in future studies. In addition, we expect the analysis of neurophysiology and inflammatory mediators before and after RIC to provide some preliminary information regarding the mechanism by which RIC promotes neuroplasticity and improves effects of training. Finally, as a safety precaution, we will monitor beat-to-beat changes in heart rate (HR), blood pressure (BP) and oxygen saturation (SaO_2) during RIC, since damaged autonomic nervous system (ANS) in individuals with SCI might dysregulate those hemodynamic responses toward the ischemic stimulation. As far as we know, this will be the first study in the SCI population (1) to investigate the synergistic effects of RIC with physical training on corticospinal excitability, (2) to measure changes in inflammatory mediators after RIC, and (3) to observe in real time the responses of HR, BP and SaO_2 during RIC.

Approach

Overview

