Data analysis: Given the previous data from the [name] Lab indicating that TLR signaling is elevated in persons with chronic SCI and the data from able bodied persons that RIC reduces TLR signaling, we will first profile expression of genes related to TLR signaling in the current participants using qPCR profiling. Briefly, RNA will be isolated from whole blood collected in PAXgene tubes (PreAnalytix, BD), using standard methods and the manufacturer's protocol (Qiagen QIAcube, Venlo, The Netherlands). RNA quality and quantity will be determined using the Bioanalyzer (Agilent). As per standard Qiagen's instructions, RNA will be converted to cDNA using the RT² First Strand Kit will be used to prepare cDNA, which is then mixed with RT² SYBR Green Mastermix. We will use the PCR Array for Human Toll-Like Receptor Signaling Pathway (Qiagen, USA) on the Roche Lightcycler 480 (384-well block). Relative gene expression will be determined using the delta delta Ct method.

Statistical analysis: A three-way 2 by 2 by 2 mixed model ANOVA will be performed for 2 within group factors (baseline vs. post-RIC) (active vs. shame) and one between group factor (able-bodied vs. cSCI) to compare the gene expression intensity. If the data is not normally distributed and the assumptions of the ANOVA are not met, Wilcoxon signed rank tests will be used instead. Post hoc pairwise comparisons will be performed using the Bonferroni adjustment, if there are any main or interaction effects within the three independent variables (group, active/sham RIC and baseline vs. post-RIC).

Potential Pitfalls/Alternative approaches/Future Directions: We propose to use standard gene expression profiling techniques and we do not anticipate technical difficulties with the approach. If we do not observe changes in gene expression of the TLR signaling pathway, we can use RNA from the samples for RNA-seq to obtain a broader and unbiased gene expression profile. Initial RNA-seq runs could be limited to 8 million reads/sample, 100bp single end, which would yield a general overview of relative changes in gene expression of the high to moderately expressed genes. If the initial pilot data look promising, then we would seek funding to perform a fuller RNA-Seq profiling.

Aim 3: To determine changes in heart rate (HR), blood pressure (BP) and oxygen saturation (SaO₂) during active versus sham RIC in individuals with incomplete cSCI and able-bodied subjects.

[figure not shown]

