Hypothesis 3A: There will be no difference in HR, BP and SaO₂ (pulse oximeter on the finger of the target arm) responses among baseline, inflation phase, deflation phase and post-RIC during active and sham RIC in persons with SCI and able-bodied controls.

Although RIC has been shown to be safe in the healthy able-bodied population as well as in individuals with heart disease and critically ill patients with subarachnoid hemorrhage^{39,40,59}, there are no data describing the safety of RIC in persons with SCI. The SCI population, particularly those with cSCI, have widespread sensory impairment, including a limited ability to feel pain/discomfort. In addition, damage to the ANS after cSCI contributes to cardiovascular dysregulation and may alter hemodynamic responses to RIC. Several studies⁶⁰⁻⁶³ have reported stable HR and BP responses before and after RIC not just in healthy participants but also in participants with heart diseases or vascular stenosis. The BP responses even remained unchanged during the whole course of RIC in able-bodied participants and in participants with stable angina pectoris^{60,62}. However, the sympathetic hypoactivity after cSCI might result in altered or delayed hemodynamic responses, possibly leading to fluctuation of HR and BP. Therefore, we will real-time record HR, BP and SaO_2 on the contralateral arm and document the pain scale and any adverse effects during RIC.

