Method: During the 50-minute active and sham RIC (5 cycles of 5 min inflation plus 5 min deflation), beat-to-beat HR, RR and SaO_2 will be monitored in real-time and digital signals will be stored on a computer hard-drive for subsequent analysis. **Electrocardiogram** - A 3-lead ECG (UFI: model RESP 1, Morro Bay CA) will be used to measure beat-to-beat HR during testing. Electrodes will be placed at the right and left clavicle and in the V-5 position; data will be recorded from V-5. **Finger Arteriolar Blood Pressure** - Beat-to-beat BP will be continuously monitored from the left middle or ring finger using photoplethysmography (FMS: Finometer, Pro; Amsterdam, Netherlands). HR and finger arteriolar BP will be viewed in real time on a computer screen and will be stored for offline analysis using customized programs written with LabView graphical software. **Brachial Blood Pressure and Oxygen Saturation (SaO_2)** - Brachial BP and SaO_2 will be measured by a trained technician using a standard adult BP cuff (GE Healthcare Information Technologies, Milwaukee, WI) with a finger pulse oximeter at 1 minute intervals during administration of the sham and RIC conditions. The peak HR, BP and the minimal SaO_2 in baseline, inflation phase, deflation phase and post-RIC will be reported for statistical analysis.

Statistical analysis: Changes from baseline in HR, BP and SaO_2 will be compared following RIC and Sham conditions in the cSCI and Able-bodied groups separately using a 2 (RIC, Sham) by 4 (baseline, inflation, deflation and post-RIC) repeated measures ANOVA to measure the hemodynamic responses for the within subject variability, and to determine main and interaction effects with Tukey post-hoc analyses. If the data is not normally distributed and the assumptions of the ANOVA are not met, Wilcoxon signed rank tests will be used instead. Post hoc pairwise comparisons will be performed using the Bonferroni adjustment, if there are any main or interaction effects within the two independent variables. The pain scale will be also compare with the same ANOVA model.

Project timeline

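### Aim 3 analyses the cSCI and able-bodied groups separately, so the plan gives no estimate of whether cSCI changes the haemodynamic response to RIC

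*Combined protocol and SAP*

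**What the plan says.** Under Aim 3, Statistical analysis, the combined protocol and SAP has changes in HR, BP and SaO2 "compared following RIC and Sham conditions in the cSCI and Able-bodied groups separately". The model is a "2 (RIC, Sham) by 4 (baseline, inflation, deflation and post-RIC) repeated measures ANOVA", so both of its factors are within-participant. Post hoc comparisons follow "if there are any main or interaction effects within the two independent variables", which are condition and phase. If assumptions fail, "Wilcoxon signed rank tests will be used instead". The pain scale is analysed with the same model.

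The reason for these measurements appears in two places. The Innovation section says that the "damaged autonomic nervous system (ANS) in individuals with SCI might dysregulate those hemodynamic responses toward the ischemic stimulation". The Aim 3 rationale says that "damage to the ANS after cSCI contributes to cardiovascular dysregulation and may alter hemodynamic responses to RIC" and that "the sympathetic hypoactivity after cSCI might result in altered or delayed hemodynamic responses".

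The Aim 3 statement covers able-bodied subjects as well as people with cSCI. The Approach section recruits 8 participants with cSCI and 8 age-matched controls. In Aim 1 the mixed ANOVA has group as its first factor. The Aim 2 model has "one between group factor (able-bodied vs. cSCI").

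**The concern.** Words such as altered, delayed and dysregulated imply a comparison with people whose autonomic system is intact. The study recruits such people and records the same signals in them, yet no Aim 3 analysis puts the two groups in one model. Group is not a factor, it is not among the variables for post hoc testing, and the signed rank fallback is a paired test that cannot compare independent groups.

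The control recordings therefore yield no planned estimate of what cSCI adds to, or takes from, the response. A reader who wants that answer has two sets of within-group p-values and whatever descriptive figures are reported. Comparing the p-values is a natural shortcut but not a test of a difference, and with 8 per group it can mislead in both directions.

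**Working it through.** **Structure.** Set side by side, the three analysis plans are:

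- Aim 1: group (2) by condition (2) by time (3), mixed ANOVA; group included.
- Aim 2: group (2) by condition (2) by time (2), mixed ANOVA; group included.
- Aim 3: condition (2) by phase (4), run once per group; group absent.

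This comparison alone establishes the point. The arithmetic below only shows how far the p-value shortcut could mislead.

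**Inputs.** From the Approach section: n = 8 per group. The documents give no alpha, power, effect size or SD for Aim 3, so there is no stated figure to reproduce. Assumed: two-sided alpha 0.05, independent groups, and effects in SD units. For the single contrast, the SD is that of a participant's active-minus-sham difference. For the simulated F test, it is the SD of the active-minus-sham difference within a phase.

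**Split verdicts when the true response is the same in both groups.** If each within-group test has power p, the chance that exactly one is significant is 2p(1 − p). For a single contrast, p comes from the noncentral t with n = 8. For the planned condition-by-phase F test (3 and 21 df), the proportion was simulated with 20,000 runs, spherical errors and an effect in the inflation phase only.

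| Common true effect | p, single contrast | 2p(1 − p) | Split verdicts, planned F test |
|---|---|---|---|
| none | 0.050 | 9.5% | 9.7% |
| 0.5 SD | 0.232 | 35.6% | 23.5% |
| 0.8 SD | 0.496 | 50.0% | not run |
| 1 SD | 0.681 | 43.5% | 48.9% |
| 1.25 SD | 0.856 | 24.6% | 45.5% |
| 1.5 SD | 0.951 | 9.3% | 29.9% |

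Worked rows: 2 × 0.05 × 0.95 = 0.095; 2 × 0.496 × 0.504 = 0.500. The maximum of 2p(1 − p) is 50%, at p = 0.5. The proportion falls again when effects are large enough for both groups to be significant nearly always.

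**Direct test.** In the same simulation, the group-by-condition-by-phase F test (3 and 42 df) was significant in 4.8% to 5.2% of runs when the groups truly responded alike.

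**A real difference missed.** With true responses of 3 SD and 2 SD, the separate F tests are significant in about 100% and 97.5% of runs, so the verdicts differ in only 2.5%. The direct F test detects this 1 SD difference in about 25% of runs. That is still low, but it comes from a valid test.

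**What 8 versus 8 can deliver.** For a two-sample comparison of one contrast (14 df), power is 46% for a 1 SD group difference and about 80% for 1.5 SD. The three-way F test has about 26%, 53% and 80% power for a group difference of 1, 1.5 and 2 SD in one phase. The 95% CI half-width for the contrast is 2.145 × √(2/8) = 2.145 × 0.5 = 1.07 SD.

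**The case against.** The strongest reply is that the analysis fits the aim as written. Hypothesis 3A predicts no difference across phases during active and sham RIC in each population, and it states no between-group contrast. The hypotheses in Aims 1 and 2 do say that trends will be similar in the two groups, and those are the aims whose models carry group. The rationale also states that safety data for RIC in SCI are lacking. That is a question within cSCI, and the cSCI-only ANOVA addresses it, together with recording of pain and adverse effects. All of this stands.

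A reader might infer more: that the safety concern goes untested, or that the plan intends to claim a group difference when one group is significant and the other is not. The documents support neither. Active versus sham is tested within cSCI, nothing in the plan announces inference from split p-values, and group summaries could be compared descriptively. Nor should the 50% figure be quoted alone. It is the maximum of the formula, and if Hypothesis 3A is true and RIC produces no response, the figure is about 10%.

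The reply does not remove the gap. The rationale raises the possibility that cSCI changes the response, the controls are measured, and no planned estimate uses them for that question. Low power does not defend the split either, since each separate analysis also rests on 8 participants and gives no group estimate.

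**Conclusion.** The point holds as a gap in what Aim 3 estimates. Active versus sham RIC is tested within each group; whether cSCI modifies that effect is neither tested nor estimated. The mismatch is with the rationale, the recruitment of controls and the models of Aims 1 and 2, not with the wording of Hypothesis 3A. The structural conclusion needs no assumption.

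The size of the hazard does need assumptions. If group differences were read from split verdicts, equal true responses would produce one in about 10% of trials with no effect and up to about 50% with a moderate effect, at alpha 0.05 and the assumed effect sizes. A direct interaction test keeps that error near 5%. This is a low-cost improvement to a non-primary aim of a proof-of-concept study; the primary MEP outcome is unaffected.

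**What to change.** Keep the per-group results and add the following to Aim 3:

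- Add group as a between-participant factor, giving a 2 × 2 × 4 mixed ANOVA. Make the group-by-condition-by-phase interaction the single group test for each outcome.
- Name one contrast: the between-group difference in active-minus-sham change from baseline to inflation, reported with a 95% CI. Treat the other phases as descriptive.
- State that any remark on group differences rests on these two results, not on a comparison of within-group p-values.
- Give a fallback that can compare independent groups, for example the rank-sum test on the named contrast, because the signed rank test cannot.

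Separate group tests at each phase would be a poor substitute. Three outcomes at three phases make nine tests, and with no true difference the chance of at least one false positive is 1 − 0.95⁹ = 37% if they are independent (less if correlated). One test for each of three outcomes gives 1 − 0.95³ = 14% on the same basis, so the results should still be labelled exploratory.

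The cost is one added analysis on data already collected, with no extra visits or participants. The downside is low precision: about 46% power for a 1 SD difference and a half-width of about 1.07 SD. The plan should say that a non-significant group result does not show that responses are similar or that RIC is safe in cSCI.

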We propose a randomized crossover study to compare active versus sham RIC combined with one bout of isometric hand exercise. Participants will be randomly assigned the order of the two experimental sessions: active or sham RIC. The isometric hand exercise will be performed in both sessions. The washout period between the two experimental sessions will be two to three weeks to prevent any carry-over effects. Figure 1 outlines the experimental protocol. Each session will consist of a pre-test measurement (baseline), active/sham RIC, post-RIC measurement, an isometric hand exercise and a post-exercise measurement. The total time in each session is around 3 hours including preparation. At the beginning and end of active/sham RIC, blood samples will be collected to measure changes in inflammatory mediators.

[figure not shown]

Figure 1. The experimental protocol.

Participants with chronic cSCI (n=8, ASIA Impairment Scale (AIS) A-D) and age-matched (within ± 5 years) able-bodied controls (n=8) will be recruited. Participants with cSCI must have at least partial ability to make volitional finger opposition movements (thumb and index finger) in at least one hand. Participants will be excluded if they have concurrent serious medical illness, traumatic brain injury, cardiovascular or pulmonary complications, seizure history, deep vein thrombosis, or any other issues that would increase risk of magnetic or electrical stimulation required for outcome measure assessment. We will also document medications that participants are currently using for systemic inflammation, spasticity, anxiety, or depression, which could affect nervous system excitability. One screening session will be conducted to confirm eligibility and determine the target arm in each participant. The arm with consistent responses on abductor pollicis brevis muscle (APB) induced by magnetic or electrical stimulation will be the target arm. Transcranial magnetic stimulation (TMS) will be performed to determine each subject's optimal scalp location for hand motor cortex stimulation, and to determine resting motor threshold for the APB muscle. Participants will be withdrawn if TMS-induced motor evoked potentials (MEPs) are unable to be detected at the APB muscles on either hand at stimulus intensity below 90% of maximal stimulator output. More details regarding inclusion and exclusion criteria are listed in the human subject section.

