Statistical Analysis: Electrophysiological outcomes will be compared after RIC and after the isometric hand exercise relative to baseline values. Descriptive analysis will be computed first for all outcomes variables to test the distribution of the data and correlation tests will be performed to check the independence among the outcome variables. A three way 2 (cSCI, able-bodied) by 2 (RIC, sham) by 3 (post-RIC, post-RICx-0, post-RICx-15) mixed-ANOVA will be used to analyze MEP₁₂₀ and intra-cortical facilitation/inhibition. If the data is not normally distributed and the assumptions of the ANOVA are not met, Wilcoxon signed rank tests will be used instead. Post hoc pairwise comparisons will be performed using the Bonferroni adjustment, if there are any main or interaction effects within the three independent variables (group, active/sham RIC and time points).

Potential Pitfalls/Alternative approaches/Future Directions: Applying RIC on motor task learning is relatively new area with little preliminary data – therefore, our primary hypothesis that RIC may promote motor task learning via increasing corticospinal excitability is highly speculative. Additionally, the effects of RIC and acute post-exercise facilitation have mostly been shown in able-bodied participants, and there are no published data in the SCI population that measured corticospinal excitability as a mechanism for acute post-exercise facilitation. Therefore, individuals with SCI might demonstrate uncertain responses toward RIC and the isometric hand exercise than that exhibited in able-bodied participants. The inconsistent injury level and the residual nerve circuits among participants with cSCI might result in the wide variability of the outcomes. Nevertheless, although our hypotheses are speculative, the proposed study is designed to provide clear answers via observing the responses in participants with cSCI and able-bodied participants. If this brief isometric hand exercise cannot lead to significantly increased MEPs in participants with cSCI, our next step might test RIC in combination with more advanced interventions such as non-invasive paired stimulation, a technique that our research team is actively studying in other protocols. Finally, if the pilot study shows a significant synergistic effect of RIC on the isometric hand exercise task, our future goal will be coupling RIC with more prolonged rehabilitation training to promote long-term effects.

[figure not shown]

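### Aim 3 specifies only a comparison of group means for its haemodynamic outcomes, which would usually miss a large reaction in one or two of 8 cSCI participants; an individual-level summary should be added.

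*Combined protocol and SAP*

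**What the plan says.** The Aim 3 Statistical analysis compares HR, BP and SaO2 "in the cSCI and Able-bodied groups separately", "using a 2 (RIC, Sham) by 4 (baseline, inflation, deflation and post-RIC) repeated measures ANOVA". Tukey and Bonferroni post hoc comparisons follow. If the ANOVA assumptions fail, "Wilcoxon signed rank tests will be used instead". The pain scale goes through the same model.

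The inputs are defined in the Aim 3 Method: "The peak HR, BP and the minimal SaO_2 in baseline, inflation phase, deflation phase and post-RIC will be reported for statistical analysis". Each participant therefore contributes one extreme value per phase and condition.

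Hypothesis 3A is that responses do not differ across phases during active and sham RIC, in either population. The rationale below it says that "there are no data describing the safety of RIC in persons with SCI", and adds: "However, the sympathetic hypoactivity after cSCI might result in altered or delayed hemodynamic responses, possibly leading to fluctuation of HR and BP".

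Other safeguards are described. The Innovation section presents beat-to-beat monitoring as a safety precaution. The Aim 3 rationale provides for recording pain and any adverse effects. The Method has HR and finger BP watched live, with brachial BP and SaO2 read every minute. The Project timeline has the team looking at participants' responses as the study proceeds. The Approach section gives 8 participants with cSCI, AIS grades A to D, and 8 able-bodied controls.

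**The concern.** Where autonomic control is damaged to differing degrees, a safety question is partly about individuals: did anyone have a large excursion in BP or HR while the cuff was inflated? A test on means answers a different question, whether the average participant shifted. At n = 8 the two can come apart badly, because one participant's large reaction raises the error term along with the mean.

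The plan gives no threshold, no count of participants with an extreme response and no per-participant display. Hypothesis 3A has no margin either, so a non-significant result invites the reading that RIC left haemodynamics undisturbed. The authors state that safety data in this population are lacking, so later studies may rely on that reading.

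**Working it through.** **Inputs.** From the documents: n = 8 per group, groups analysed separately, a 2 x 4 within-participant design, hence 1 and 7 df for condition and 3 and 21 df for phase and for the interaction. The plan gives no alpha, SD, effect size or power for Aim 3, so there is no planned figure to reproduce. Assumed: alpha 0.05; independent normal noise with cell SD 5 to 12 mmHg; a reaction during active inflation only.

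**Limit for a large reaction.** Let k of 8 participants react by D and the rest not at all. The mean reaction is kD/8 and the sum of squares about it is kD²(8 - k)/8. For any effect that the reaction touches, as D outgrows the noise,

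F → 8 × 7 × (kD/8)² / [kD²(8 - k)/8] = 7k/(8 - k).

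D cancels. Keeping baseline as a level while analysing changes from baseline does not alter this limit.

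| Reactors k | Limiting F | p on 1, 7 df | p on 3, 21 df |
|---|---|---|---|
| 1 | 7/7 = 1.00 | 0.35 | 0.41 |
| 2 | 14/6 = 2.33 | 0.17 | 0.10 |
| 3 | 21/5 = 4.20 | 0.08 | 0.018 |

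The 5% critical values are 5.59 and 3.07. One or two reactors fall short in the limit on every test. Three exceed the uncorrected 3, 21 df value.

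**Realistic noise.** Simulated 2 x 4 ANOVAs, 20,000 per scenario, no sphericity correction (the plan mentions none):

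| Scenario (cSCI, n = 8) | Each F test significant | At least one of three significant |
|---|---|---|
| No reaction | about 5% | about 14% |
| One reactor, 40 mmHg | 3-5% | about 10-14% |
| One reactor, 80 mmHg | 0.4-4.5% | about 1.5-12% |
| Two reactors, 40 mmHg | 7.5-14% | about 24-32% |

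With one reactor, a significant result is no more likely than with none, and doubling the surge makes it less likely. With two, the chance rises above the no-reaction rate, but about 68-76% of trials still show nothing significant.

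**Signed-rank fallback.** At n = 8 the exact two-sided 5% test rejects when the smaller rank sum is 3 or less. Five sets of ranks meet that: none, {1}, {2}, {3} and {1, 2}. With no reaction the rejection probability is 2 × 5/2⁸ = 3.9%. One large reactor fixes rank 8 as positive, giving 5/2⁷ = 3.9%. Two fix ranks 7 and 8, giving 5/2⁶ = 7.8%. These are before any Bonferroni adjustment.

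**What a count would show.** Exact 95% intervals: 0 of 8, upper limit 1 - 0.025^(1/8) = 36.9%; 1 of 8, 0.3% to 52.7%; 2 of 8, 3.2% to 65.1%. If the true reaction rate is 10%, the chance of seeing at least one reactor among 8 is 1 - 0.9⁸ = 57%; at 25% it is 1 - 0.75⁸ = 90%.

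**The case against.** The best case for the plan is that it has more than a p-value. Participants are watched in real time, adverse effects are documented, responses are examined as the study proceeds, and individual peaks and minima are already extracted. A reader might infer that RIC safety is judged by the ANOVA alone. The documents do not say so. What stands is narrower: no supplied passage defines a haemodynamic event or says how such records bear on 3A.

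A reader might also infer that 3A would be declared upheld despite an extreme reaction. No rule in the plan turns non-significance into confirmation. Nor do the documents say that a symptom-free surge would go uncounted as an adverse effect. They do not define the term, and the human subject section they cite is not in the supplied text.

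Three statistical objections are fair. The ANOVA is not blind to two reactors, as the 24-32% shows. The signed-rank test does use magnitude through ranks, and loses only the size beyond the top rank. A confidence interval for the mean contrast would also give some warning: with one 80 mmHg surge and cell SD 5 mmHg, its half-width grows from about 8 to 25 mmHg. But no such interval is specified for Aim 3, and it would not show who reacted or how many did.

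Finally, the remark that "The inconsistent injury level and the residual nerve circuits among participants with cSCI might result in the wide variability of the outcomes" comes from the Aim 1 pitfalls and concerns corticospinal outcomes, so it is not evidence about haemodynamics. The Aim 3 rationale describes a feature of the cSCI population, for which a mean comparison is a reasonable first description. That is a reason to keep the ANOVA, not to rely on it alone.

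**Conclusion.** The point holds in limited form. The only analysis specified for the Aim 3 haemodynamic outcomes compares group means at n = 8 per group, with no individual-level summary and no margin. It would almost always give no sign of one extreme reactor beyond the chance rate of significance, and would usually miss two. The limiting results rest on alpha 0.05 and equal reactions; unequal or opposite reactions give a smaller F. The simulated rates also rest on the assumed SDs and independent noise.

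The stronger claims, that safety rests on the ANOVA alone or that a reaction would necessarily go unrecorded, are not supported. This is an inexpensive improvement to the analysis plan rather than a defect in conduct, and it is worth making because the authors say that no safety data exist in this population.

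**What to change.** 1. Keep the 2 x 4 ANOVA as a description of the mean response.
2. Add a table or plot of each participant's change from baseline in peak HR, peak BP and minimum SaO2, by phase, for active and sham.
3. Report, for each group, the number of participants whose change exceeds a limit that the investigators fix before examining the data, with exact 95% confidence intervals. The Project timeline starts analysis after the first two or three participants, so the limit needs to be recorded before then.
4. State with Hypothesis 3A that a non-significant mean difference does not show absence of individual reactions, and say how documented haemodynamic events will enter the Aim 3 conclusion.

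The cost is some wording and one extra table from data already recorded. The one drawback is candour about precision: a clean 0 of 8 must be reported with its upper limit of 37%.

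### Aim 3's signed-rank fallback has no workable multiplicity rule: with 8 per group, Bonferroni over 7 or more comparisons can never reach significance, and no adjustment leaves error uncontrolled

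*Combined protocol and SAP*

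**What the plan says.** In the combined protocol and SAP, the Approach overview sets the size: "Participants with chronic cSCI (n=8, ASIA Impairment Scale (AIS) A-D) and age-matched (within ± 5 years) able-bodied controls (n=8) will be recruited".

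The Statistical analysis paragraph under Aim 3 compares changes from baseline between conditions "in the cSCI and Able-bodied groups separately using a 2 (RIC, Sham) by 4 (baseline, inflation, deflation and post-RIC) repeated measures ANOVA". The endpoints are extremes within each phase: "The peak HR, BP and the minimal SaO_2 in baseline, inflation phase, deflation phase and post-RIC will be reported for statistical analysis". The pain scale goes through the same model.

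The fallback is: "If the data is not normally distributed and the assumptions of the ANOVA are not met, Wilcoxon signed rank tests will be used instead". The next sentence reads: "Post hoc pairwise comparisons will be performed using the Bonferroni adjustment, if there are any main or interaction effects within the two independent variables". The same paragraph also names another post hoc method for the ANOVA: "to determine main and interaction effects with Tukey post-hoc analyses".

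Hypothesis 3A is a null statement, "There will be no difference in HR, BP and SaO₂", across the four phases under active and sham conditioning in both groups.

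The document gives no alpha, no sidedness, no list or number of comparisons and no equivalence margin. It does not say whether the signed-rank p-values are exact, or whether Bonferroni covers the fallback tests.

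**The concern.** A signed-rank test compares two sets of paired values. It gives no omnibus test of condition, phase or their interaction. Once the fallback replaces the ANOVA, nothing remains that could satisfy the condition for the Bonferroni step. The analyst must then choose between two readings, and both can go badly wrong at this sample size.

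- **Adjust anyway.** The exact signed-rank p-value has a floor set by the number of pairs. With 8 pairs that floor is high enough for a moderate Bonferroni family to put the threshold out of reach.
- **Do not adjust.** Many pairwise tests per variable and group are run at the full alpha.

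This matters because Aim 3 is the plan's haemodynamic safety question. The background to Hypothesis 3A says that safety data for conditioning after spinal cord injury are lacking, and the hypothesis is that nothing changes. A procedure that cannot reject would look like support for it. The fallback is also a realistic branch: the endpoints are peaks, minima and a pain score in 8 people.

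**Working it through.** The plan states no power, alpha or sample-size figure, so there is none to reproduce.

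**Inputs.** From the document: 8 participants per group, groups analysed separately, 2 conditions x 4 phases = 8 cells. Assumed: two-sided alpha 0.05 and exact p-values with no ties or zero differences.

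**Step 1: the floor.** With n pairs there are 2^n equally likely sign patterns. The most extreme result, all differences in one direction, has two-sided p = 2/2^n. For n = 8 this is 2/256 = 0.0078. The next values are 0.0156 (W = 1), 0.0234 (W = 2), 0.0391 (W = 3) and 0.0547 (W = 4), where W is the smaller rank sum.

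**Step 2: candidate families, per variable and group.**

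| Comparisons | k | 0.05/k | Reachable at n = 8? |
|---|---|---|---|
| Active vs sham change from baseline, 3 later phases | 3 | 0.0167 | Yes, W = 0 or 1 |
| Active vs sham at each phase | 4 | 0.0125 | Only W = 0 |
| All pairs of 4 phases | 6 | 0.0083 | Only W = 0 |
| Smallest failing family | 7 | 0.0071 | No |
| Phase pairs within each condition, 6 x 2 | 12 | 0.0042 | No |
| Those plus active vs sham at each phase, 12 + 4 | 16 | 0.0031 | No |
| All pairs of 8 cells, 8 x 7/2 | 28 | 0.0018 | No |

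Hypothesis 3A, read directly, compares the four phases under each condition. That is the family of 12, twice the largest workable size of 6.

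**Step 3: power where the test can work.** Power was simulated with 200,000 draws of normal paired differences, n = 8. The chance of W = 0, which is the power at k = 4 to 6, is shown beside a paired t-test at 0.05/6.

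| True difference, in SDs of the paired difference | Signed-rank, W = 0 | Paired t at 0.05/6 |
|---|---|---|
| 0.5 | 5% | 6% |
| 1.0 | 25% | 32% |
| 1.5 | 58% | 71% |
| 2.0 | 83% | 94% |

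At k = 3, signed-rank power for a 2 SD difference is about 95%. At k = 7 or more it is 0% for any difference.

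**Step 4: no adjustment.** With 20,000 null runs, independent normal cells and n = 8, the family-wise error is about 33% for 12 tests, 39% for 16 and 52% for 28. It is about 10% for the three change-from-baseline contrasts and 15% for active versus sham at four phases.

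**Step 5: sensitivity.**

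- n = 7: floor 2/128 = 0.0156, so k can be at most 3.
- n = 6: floor 2/64 = 0.031, so k = 1 only.
- n = 5: floor 2/32 = 0.0625, so nothing is reachable.
- One-sided, n = 8: floor 1/256 = 0.0039, so k can be at most 12.
- Normal approximation, n = 8: smallest p 0.0117, so k can be at most 4. With continuity correction it is 0.0143, so k can be at most 3.

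The effective n could fall below 8 through dropout or zero differences. Zeros are plausible for a pain score or for saturation in whole percent, though the document does not state the resolution. The Aim 3 statement also refers to incomplete injury while recruitment allows AIS A to D, so the cSCI set for this aim could be smaller than 8.

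**The case against.** The strongest reply is that the decisive number, the size of the Bonferroni family, is not in the document. The paragraph speaks of changes from baseline compared between conditions, and one natural reading of that is three contrasts, which are testable. Of the 28 cell pairs, 12 differ in both condition and phase, and no hypothesis asks about them. All of this stands. Impossibility is therefore conditional on a family of 7 or more, and the 52% error rate on testing all 28 pairs.

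It is also fair that the ANOVA is the planned analysis and has no such floor, and that the fallback applies only when its assumptions fail. Safety does not rest on this p-value alone either: the signals are watched in real time, and pain and adverse effects are recorded. Reading non-significance as no difference is a weakness of the ANOVA branch too.

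Two stronger inferences are tempting. The first is that almost no Aim 3 comparison can ever be significant, so that the predicted result is guaranteed. The documents do not support it: the ANOVA can reject, families of up to 6 can reject, and an unadjusted fallback rejects too often. The second is that the same floor blocks a cSCI-only comparison in Aim 1. Aim 1 uses the same sentence pair, "Wilcoxon signed rank tests will be used instead. Post hoc pairwise comparisons will be performed using the Bonferroni adjustment", but it plans one model with both groups together and no separate cSCI test. Active-sham pairs over all 16 participants have a floor of 2/65,536.

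What the reply does not remove is the undefined trigger. The text ties adjustment to effects that the fallback cannot produce, and the most direct reading of Hypothesis 3A gives 12 comparisons.

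**Conclusion.** The point holds for the Aim 3 fallback only. As written, the fallback has no defined multiplicity rule. At two-sided 0.05 with exact tests and 8 complete, non-zero pairs, Bonferroni over 7 or more comparisons cannot give a significant result. Over 4 to 6 it needs all 8 participants to move in one direction. Without adjustment, null family-wise error is about 33% for the 12 comparisons that Hypothesis 3A implies, and runs from about 10% for 3 to 52% for 28. So for the same data the result depends heavily on a choice that the plan leaves open.

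The figures rest on an assumed alpha and sidedness, an assumed family size and, for the error rates, independent normal cells. The floor itself is exact. Any loss of pairs tightens the limit.

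**What to change.** Rewrite the fallback in the Aim 3 Statistical analysis paragraph. State alpha and sidedness, and that p-values are exact. Keep one post hoc method for the ANOVA in place of both Tukey and Bonferroni. Remove the main-or-interaction condition from the fallback and adopt one of these:

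1. **Named contrasts.** List at most 6 contrasts per variable and group, tested by signed rank with Bonferroni over that list. Active versus sham change from baseline at each of the three later phases is a good choice, because 3 contrasts remain testable if one pair is lost.
2. **Sign-flip permutation with max-T.** Flip the signs of each participant's whole set of contrasts together, over all 256 patterns, and refer each contrast to the distribution of the maximum statistic. The adjusted p can reach 0.0078 however many contrasts are listed. In simulation (600 and 1,000 runs) its power for a 2 SD active-sham difference at inflation was 79% to 81% over 16 contrasts, where signed-rank with Bonferroni has 0%. Option 1 with 6 contrasts gives about 82% to 83%, so max-T is needed only if the longer list is wanted.

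Under either option, and for the ANOVA as well, report each Aim 3 contrast with its estimate and 95% CI, so that a non-significant result is not taken as evidence of no difference.

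The cost is a few sentences in the SAP and no new data. The downside is fewer formal comparisons under option 1, or a little more code under option 2.
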